3.0 Objectives

The overall objective of our mixed method study is to evaluate a strategy to improve the quality and clinical usefulness of 'the 5th Vital Sign' in VA primary care. We will first develop a patient-self administered computer-aided pain assessment, then evaluate and refine the assessment using human-computer interaction laboratory usability testing. Next we will conduct a three site randomized controlled trial (RCT) to test a computer-based pain assessment protocol compared with usual pain screening. In the RCT we will evaluate three arms – one arm will use the PEG, a more sensitive screener including pain functional impairment, and a second arm will replicate the 'NRS now' allowing a direct comparison of patient-administered assessment vs. clinician assessed pain and a third arm will test the NRS at one week. All subjects will be screened with the '5th Vital Sign'. (allowing a three arm comparison of each of two computer based approaches vs. usual practice) Our specific aims are to:

Aim 1. Characterize primary care team perspectives on enhanced pain screening approaches compared with usual pain screening, including clinical usefulness and how to use skills, roles, and tasks of multidisciplinary primary care clinicians and consultants to optimize pain care. Additionally, we will try to understand Veterans' experiences with pain screening, assessment, and management (including use of opioid analgesics) in order to better link their actual experience with provider assessment and management practices. Interviews and focus groups will inform refinement of the items and screening interface; we will evaluate the interface including the PEG and 'NRS now' and the control arm for usability including among disabled veterans and for use in primary care.

Aim 2. Evaluate in a three-arm RCT the effects of enhanced pain screening approaches using a tablet and comparing the PEG, the 'NRS pain now', and usual clinician-assessed pain screening.

Hypothesis 2a: One of three enhanced pain screening approaches using the PEG, but not the 'NRS now' will be associated with improved detection of pain related disability **Hypothesis 2b:** Enhanced pain screening approaches vs. usual pain assessment will be associated with equally low missingness, Veterans, providers, and clinic and facility staff will characterize their experience with the enhanced screening protocol and important barriers, facilitators, and practical steps to inform implementation

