In general, we will solicit a visit-based sample of Veterans at each site so that we can ensure diversity in the population of Veterans and to minimize biases in our recruitment procedures. We plan to enroll approximately 650 participants among all three sites combined. We will recruit no more than 2000 respondents.

After a brief run-in phase, patients presenting in specified primary care clinics in the Palo Alto, Portland, and Minneapolis VAs will be asked to complete the survey on a tablet before vital signs are taken by clinic staff.

a. Participant Eligibility:

Veterans are eligible if they are attending a clinic visit in a participating primary care clinic and will have their vital signs taken as part of that visit and are not otherwise determined to be ineligible.

Veterans would be determined ineligible if they are:

- Severely visually impaired
- Incapable of rationale responses
- Physically unable to manipulate/control the tablet (unless a proxy is present and willing to input the Veteran's responses)

b. Recruitment

The primary recruitment will take place in the primary care clinics by trained research assistants approaching Veterans after they have checked in for their appointment. If a veteran expresses interest in participating, they will be informed of the study and screened for eligibility. All veterans approached by clinic staff will receive an anonymous study identification. Research staff will recruit in clinics for full or half-days selected from within the study enrollment window. A Research Assistants will use a 'Next Available' method of randomizing which Veterans will be approached (i.e., When the R.A. is ready to begin/resume recruitment the next patient that completes the check in process for the clinic will be approached.)

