The 1 page field log will contain both identifiable (i.e., Full Name, last 4 digits of SSN, and contact information as needed for participation in follow up interviews) and unidentifiable data (i.e., participation status, participant ID, and observable demographics when necessary, and other research pertinent information). While in the clinic field logs will be kept on person by research staff and in a locking carrying case or secured mail bag to be transferred to a designated office. The paper documents will be stored in a locked filing cabinet inside of a locked office on VA campuses at the designated VA sites (i.e., Palo Alto, Minneapolis, Portland). A designated research assistant from each site will input the data into an encrypted and password protected Excel sheet that is kept on a secured server at VA Palo Alto. The designated research assistants at VA Portland VA Minneapolis will only have access to the cross-walk Excel sheet for their specific site. Research assistants from Palo Alto (i.e., [name] and [name]) will have access to a site specific Palo Alto Excel sheet and a master cross-walk Excel sheet that is populated by site specific crosswalks. Drs. [name] and [name] will have view only access to the master cross-walk excel sheet. At a later stage in the study, a designated programmer will have view only access to the master cross-walk excel sheet in order to compile data from both tablet survey data and medical records.

5. Tablet based survey content:

We will focus on content that is not available in existing VA administrative database the survey will include (not in this order):

- 1) an **introductory screen** which allow for registration using the unique participant number, and
- 2) **an algorithm corresponding to the three intervention arms of the RCT** and an underlying randomization engine to allocate Veterans to the three arms using a random number generator, with the corresponding pain screening measures (PEG, NRS one week, and DVPRS), and
- 3) The **Graded Chronic Pain Scale** (the gold standard for comparison),and
- 4) **Self-assessed level of physical activity**, and
- 5) **expectations and unmet need for pain treatment and management**, and

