- 6) **familiarity and experience with technology and satisfaction with the rating experience** including whether the veteran has previously used a tablet and environmental context because these items reflect previous concepts salient to pain rating variation, and
- 7) **access to and experience with smart mobile technology**

Depending on the consideration of survey length which we will prioritize to keep the survey at approximately 10 minutes, we will consider including several other items that previous research have shown to be important in considering pain outcomes including duration of pain in the previous year and the physical location of pain. In order to minimize survey burden and in order to complete our planned analyses, we will consider using VA data (rather than participant responses to obtain information about BMI, comorbidity, copay exemption status). We will also ensure physical attributes of the tablet screen best accommodate visually impaired and other physically disabled veterans where possible.

At the conclusion of the study in order to assess the degree to which implementation succeeded and Veterans who were missed by the tablet based protocol, we will compare all Veteran patients of the clinic during the study interval, as well as all Veterans who were approached but declined, with all Veteran users of the tablet during the same time by age, race / ethnicity, gender, cognitive impairment and mental health diagnoses, and NRS pain ratings, to assure that the tablet based screening process does not disadvantage any Veterans. We will gather these factors using VA electronic databases and will request a HIPAA authorization and waiver of documentation of informed consent for this portion of the study.

The usual care arm nursing staff rating of the 'NRS pain now' will be collected by linking the encounter to the Vital Signs Package to obtain the pain rating. Veterans' health records accessed in Corporate Data Warehouse and CAPRI/ VistAWeb/CPRS, will inform basic demographics and clinical factors in order to allow us to minimize the burden of the tablet protocol.

B. Patient Follow up Interviews:

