If possible, research staff will attend a local clinic staff meeting to briefly inform the staff of the study. By partnering with local clinic leadership, we plan to send emailed invitations to eligible staff members. A log of all contact attempts will be maintained and after a maximum of 3 contact attempts the staff member will be removed from the contact list.

2. Consent Process:

Prior to the interview, a research staff member will verbally consent the participant. We have approval for a waiver of documentation of informed consent. Date of consent and person obtaining consent will be logged on the secured Excel sheets stored on VA Palo Alto Servers.

3. Data Collection Procedures:

We will conduct up to 40 telephone interviews that will take approximately 20-30 minutes. The interviews will be audio recorded and later transcribed by a VA contracted transcription service. For interview questions/content please see the Provider Interview Protocol.

4. Data Security:

Any information linking identifiable information with an assigned participant ID will be located on the secured Excel sheets. These Excel sheets will be secured and stored as previously mentioned under Phase 2: a: Data Security.

Audio files will be uploaded to the secured server located at VA Palo Alto. The audio Files will be saved using the assigned participant id. Audio files and de-identified transcripts will be transferred between VA servers and the transcriptions service via an approved secured FTP server.

Figure 1: Estimated enrollment scheme for ESP

Due to randomization the proposed enrollment algorithm will allow analytic comparison of each assessment measure / mode to the other. The table below specifies the Arm to Arm comparisons but the outcomes of each comparison are ‘clinically significant pain’ defined as pain that is moderate to severe, pain that is associated with disability, or unmet need for additional management.

Main comparison (s) of interest		Arm (s)	Comment
1	Tablet: PEG vs. NRS 1 week vs. DVPRS	1 to 2 to 3 tablet comparison	Baseline arm to arm difference

Table 1: Main analytic comparisons by screening measure and mode for outcomes of detection of pain, detection of moderate / severe pain (clinically relevant), pain associated with disability and unmet needs for treatment

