5.3 Study Evaluations/Data Analysis

Phase	Data Type	Source	Outcome	Analyses	Comment
1	Qualitative	Multidisciplinary providers, clinic staff, and Veterans	n/a	Grounded theory	Characterize screening information use in care
			management		
1	Quantitative	Patient	Pain-related disability, detection	By intervention arm*	At screening encounter

1&2	Quantitative	Patient, linked to VA health data for Veteran demographics and clinical factors	Pain missingness,	By intervention arm*	At screening encounter
2	Qualitative	Provider, patient	Satisfaction and experiences with screening including implementation	Grounded theory	Characterize experiences with the tablet and enhanced pain screening approaches

Outcome	Measure	Analysis	Model
Immediate pain related disability	NHIS pain-related disability	Arm 1,2,3 pairwise	Linear regression, adjusted for patient factors
Immediate pain missingness	NRS (nurse), NRS (tablet), PEG (tablet);	% missing pain ratings (Arm 1,2,3)	Logistic regression, adjusted for patient, rater (tablet perception), and environmental factors

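### The only model stated for pain-related disability compares disability itself between randomised arms, so it cannot show which screener detects it better, and its measure differs from the named gold standard

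*Protocol*

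**What the plan says.** Section 3.0 (Hypothesis 2a) states that screening with the PEG, but not with the current-pain NRS, "will be associated with improved detection of pain related disability".

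The second table of section 5.3 has two model rows. The first is for immediate pain-related disability: the measure is "NHIS pain-related disability", the contrast is arms 1, 2 and 3 pairwise, and the model is "Linear regression, adjusted for patient factors". The other row is a logistic regression for missing pain ratings. The first table of section 5.3 places disability and its detection at the screening encounter, by arm. Table 1 in section 5.1 describes the comparison of the three tablet arms as "Baseline arm to arm difference".

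The tablet content in section 5.1 (Phase 2, part A, item 5) lists each arm's screener and the Graded Chronic Pain Scale, called "the gold standard for comparison". NHIS is not among the listed items; elsewhere it appears only in the reference list. The nurse's current-pain rating "will be collected by linking the encounter to the Vital Signs Package to obtain the pain rating". On size, section 5.1 says: "We plan to enroll approximately 650 participants among all three sites combined. We will recruit no more than 2000 respondents".

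**The concern.** Detection is a relation between two things: the screener result and the patient's true state. The stated model contains only the second. It has no screener score, cut-point, sensitivity, specificity or AUC. How disabled a Veteran is does not depend on which screener the tablet happened to show a few minutes earlier, so randomisation makes the arms equal in expectation.

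The one route to a real arm difference is a question-order effect, which is possible because item order is left open ("the survey will include (not in this order"). That would not measure detection either.

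If the row is followed as written, neither a null nor a significant result says which screener finds disabling pain. Hypothesis 2a, and the choice of a preferred measure that the abstract says will inform national VA implementation, would have no stated analysis behind them. Naming two different measures for the same construct adds to the difficulty, because a reader cannot tell what a screener would be judged against.

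**Working it through.** The protocol gives no power, alpha or effect size for this outcome, so there is no stated figure to reproduce. The check has four steps.

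**1. Expected value of the stated contrast.** Let D be disability and A the arm. Randomisation gives D the same distribution in every arm, and the outcome is taken at the same encounter. So E(D | A = 1) − E(D | A = 2) = 0. Screener accuracy does not enter this expression.

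**2. Simulation of the stated test.**
- From the protocol: about 650 enrolled at 1:1:1, so 650/3 ≈ 217 per arm; upper case 2000/3 ≈ 667 per arm; comparator AUC 0.78, the middle of the 0.76–0.80 in section 2.0, which was reported for the nurse NRS against the BPI.
- Assumed: two-sided 5% level; 30–50% of patients positive on the reference measure; screener scores normal with unit variance, shifted in positives by √2·Φ⁻¹(AUC), which is 1.09 for AUC 0.78 and 1.47 for AUC 0.85.

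| Per arm | AUC pairs | Test of disability by arm rejects |
|---|---|---|
| 217 | 0.82, 0.85 or 0.90 vs 0.78; 0.98 vs 0.55 | 4.5–5.4% |
| 667 | 0.82 or 0.85 vs 0.78 | 4.2–5.3% |

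There were 4,000 trials per scenario at 217 per arm and 2,000 at 667. A separate simulation with prevalence 20–40% and AUC 0.78–0.95 vs 0.78 gave 4.3–6.0%. All of these are the nominal 5% within simulation error.

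**3. What an accuracy comparison would give.** Rejection rates for an unpaired DeLong test between arms, at prevalence 30/40/50%:

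| AUC | 217 per arm | 95% half-width at 217 | 667 per arm |
|---|---|---|---|
| 0.90 vs 0.78 | 85/88/90% | 0.079/0.074/0.073 | not run |
| 0.85 vs 0.78 | 36/39/41% | 0.086/0.081/0.079 | 79/85/87% |
| 0.82 vs 0.78 | 14/16/16% | 0.090/0.084/0.082 | 35/37/40% |

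Hand check with the Hanley–McNeil formula at prevalence 40% (87 positive, 130 negative per arm): SE(0.85) = 0.0284 and SE(0.78) = 0.0333, so the SE of the difference is √(0.0284² + 0.0333²) = 0.0437. The half-width is 1.96 × 0.0437 = 0.086, z = 0.07/0.0437 = 1.60, and power ≈ Φ(1.60 − 1.96) = 36%. This is slightly below DeLong, as expected from a more conservative standard error.

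A paired DeLong comparison with the nurse NRS on the same 217 patients (0.85 vs 0.78, 3,000 trials, assumed score correlation 0.3–0.7) has power 44–83% and a half-width of about 0.05–0.075.

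**4. Could detection mean the share flagged on each arm's own screener?** Share flagged = sensitivity × prevalence + (1 − specificity) × (1 − prevalence). Take two illustrative tools at prevalence 30% and 50%:
- Sensitivity 0.90, specificity 0.60: 0.27 + 0.28 = 55%, and 0.45 + 0.20 = 65%. Youden index 0.50.
- Sensitivity 0.70, specificity 0.90: 0.21 + 0.07 = 28%, and 0.35 + 0.05 = 40%. Youden index 0.60.

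The tool with the lower Youden index flags 25–27 points more patients, because false positives count as detection. That reading does not rescue the analysis.

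**The case against.** The strongest reply is that the row is four table cells, that it is not labelled as the test of Hypothesis 2a, and that the intent to study detection is plain elsewhere. The Table 1 caption and the first table of section 5.3 both name detection, the consent section speaks of assessing how the measure performs, and a gold standard is collected. Regressing disability on the screener score within arms could be squeezed into those cells, and an asterisk beside the arm comparison has no footnote in the text at hand. Cut-points and the exact test commonly belong in an SAP, which is not shown.

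Some of this stands. The link between the row and Hypothesis 2a is inferred: it is the only disability model given, and no stated analysis relates a screener to a reference. The intent is there. But no model is attached to it, and the one model that is attached answers a different question. That is a mismatch within the protocol, not detail left for later.

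Three narrower points also stand. The protocol calls NHIS an outcome measure, not a reference standard, so the conflict is that two instruments serve one construct and one of them is missing from the listed survey content. The near-5% rejection rates follow by construction; they illustrate step 1 and do not prove it. And Hypothesis 2a contrasts the PEG with current-pain NRS, while the tablet content and Table 1 list PEG, one-week NRS and DVPRS, so a between-arm accuracy test still would not match 2a as worded until those labels are reconciled.

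**Conclusion.** The concern holds: the analysis is wrong as written and must be fixed. The conclusion that the disability row has no power for a difference in detection, at any sample size, needs only randomisation and same-encounter measurement. The power and precision figures for the alternative are illustrative. They depend on the assumed prevalence, the assumed AUCs, a comparator AUC borrowed from a different mode and reference, and, for 667 per arm, on treating the ceiling of 2000 respondents as if all were randomised. The mismatch between NHIS and the Graded Chronic Pain Scale is a plain textual inconsistency and rests on no assumption.

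**What to change.** 1. Choose one reference measure for pain-related disability, with a stated cut, and name it in both the tablet content and section 5.3. If NHIS is kept in any role, add it to the survey content.
2. Replace the analysis in the disability row with wording such as: *Accuracy of the arm's tablet screener against the reference measure: AUC, and sensitivity and specificity at a stated cut-point for each screener; arms compared pairwise with a test for independent samples (e.g. unpaired DeLong), with 95% confidence intervals.*
3. Add: *Within each arm, tablet screener versus linked nurse NRS on the same patients, by paired AUC comparison.*
4. Report mean disability by arm descriptively only. It is recorded after allocation, so it is a clean balance check only if question order has no effect; fixing the position of the reference items identically in all arms would help. Reword the Table 1 comment as a between-arm difference in screener accuracy.
5. Align the wording of Hypothesis 2a with the screeners actually allocated.
6. State the expected precision.

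No new data collection is needed if the Graded Chronic Pain Scale is the reference: it, each arm's screener and the nurse rating are already planned. The cost is a decision on the reference and the cut-points, and candour about precision. At about 217 per arm, AUC differences of 0.07 or less would probably be missed between arms; the paired comparison with the nurse rating is more precise.

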2.0 Introduction

Despite the importance of pain and widespread interest in patient-centeredness, the VA remains exceptional in emphasizing and successfully making pain and its management a routine feature of the health record and a focus of care. Awareness of pain and efforts to improve pain management rest on the VA's '5th Vital Sign' – a policy and practice of nursing staff routinely screening for 'pain now' at every health encounter using a 0-10 Numeric Rating Scale (NRS) (1).

Our team's previous research on the VA's '5th Vital Sign' informs the specific design of the ESP study as well as the proposed research products. (5-7) Our evaluation of routine pain screening practice in the VA identified some important concerns that keep the VA's '5th Vital Sign' from living up to its full promise:

- The "fifth vital sign" measure of current pain intensity, demonstrates limited accuracy leading to only moderate correspondence (e.g., ROC of 0.76-0.8 in two studies) for chronic disabling pain measured with the Brief Pain Inventory (BPI) (5,10), and
- Nursing staff who deliver pain assessment in about 50% of cases use informal, unstructured pain queries (e.g., 'Is your knee good today?') rather than adhering to formal use of the 0-10 NRS leading to pain underestimation, despite efforts to standardize assessment (5), and
- Linkage is missing between the current pain screening approach and improved care—pain screening information is passively available but seldom used by busy providers who act on moderate to severe pain with augmented management in only about 15% of cases. (6,7)

Several alternatives to the current pain screening approach (e.g., nurse administered 'NRS pain now' improve the sensitivity and specificity of screening for chronic pain – the optimal measure being a three item scale incorporating intensity and emotional and physical interference (e.g., the PEG). (6,7) The PEG includes items that assess physical and emotional interference, and it is very similar to the gold standard BPI from which it is derived in sensitivity, specificity, and sensitivity to change in detecting clinically important, functionally impairing pain. (6)

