A patient-reported approach (e.g., PRO) might be preferable to clinician screening, but these alternatives should be formally compared. On the one hand, nursing staff responsible for screening for the 'Fifth Vital Sign' screen informally which reduces screening sensitivity. (5) We found that nursing staff members' work experience, confidence in pain management, and use of informal rating contribute to pain screening variation. (11) Thus, by removing nursing staff rater variation, A PRO approach might improve standardization of the report. Other benefits could include scalability and sustainability over time including evolution consistent with automating aspects of care.

Although a PRO approach might reduce variation due to nursing staff rating factors, it could also increase variation by introducing unique issues including the specific items, mode, and context. For example, we also found in HELP-Vets that environmental context (e.g., a distracting or busy environment) contributed to pain screening variation, (11) and those could be worse depending on the physical environment of a tablet! Further underscoring the need to compare approaches, clinician documented pain could be less sensitive but more actionable (e.g., clinicians document the pain

they can do the most about), and some patients' who are challenged to self report (e.g., those with profound cognitive or visual impairment) might be best evaluated by a clinician.

In considering an enhanced pain screening solution, we will conduct a formative evaluation for more widespread implementation including consideration of the role of informatics and how to link screening-to management. (8,12) In the longer term, implementation success has to be framed in how screening improves patient outcomes – in the case of pain, through the use of meaningful metrics (e.g., functional), actionable treatment strategies, and multidisciplinary and generalist-specialist collaboration. Although it's unclear exactly how to link screening to management, clinicians need to be engaged to determine how screening information should be presented and integrated in workflow to facilitate patient outcomes.

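### The missingness model includes a nurse-recorded rating but has no nurse or clinic term, so tablet-versus-nurse results would get standard errors that are too small; contrasts between randomised arms are not affected

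*Protocol*

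**What the plan says.** The outcome table in protocol section 5.3 has two rows.

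- **Pain-related disability:** Veteran-reported, arms compared pairwise, "Linear regression, adjusted for patient factors".
- **Pain missingness:** the measures begin "NRS (nurse), NRS (tablet), PEG (tablet", the analysis is the percentage "missing pain ratings (Arm 1,2,3", and the model is "Logistic regression, adjusted for patient, rater (tablet perception), and environmental factors".

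Neither row names nurse, clinic or site. The word rater appears once and is explained as perception of the tablet.

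Section 2.0 gives the protocol's own evidence on nurses: "Nursing staff who deliver pain assessment in about 50% of cases use informal, unstructured pain queries", and their "work experience, confidence in pain management, and use of informal rating contribute to pain screening variation". Removing that variation is offered there as a reason for patient self-report.

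The comparison with the nurse is among the aims. The Abstract (Significance) promises to set patient-reported against clinician-documented pain directly. Section 3.0 says that all participants also have the usual nurse screen, and Hypothesis 2b expects missingness to be as low with enhanced as with usual assessment.

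Allocation is by individual Veteran, 1:1:1, through "an underlying randomization engine to allocate Veterans to the three arms using a random number generator" (section 5.1, Phase 2, part A, item 5). The same item links each encounter to the Vital Signs Package for the nurse's pain rating. It does not mention who made the rating.

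**The concern.** Each nurse will rate many participants. If nurses differ in how they ask and record, two Veterans seen by the same nurse are more alike in their nurse rating, and in whether it is missing, than two seen by different nurses. A logistic regression that ignores this counts 650 ratings as 650 independent pieces of information on usual screening.

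The damage falls where nurse ratings are averaged and not contrasted between arms: the tablet-versus-nurse difference and the overall nurse missingness rate. If Hypothesis 2b is tested for a difference, the false-positive rate rises. If it is read as a claim of similarity, intervals that are too narrow make similarity too easy to declare. The result is meant to inform national VA practice.

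**Working it through.** **Inputs from the protocol.** About 650 participants over three sites (section 5.1); individual 1:1:1 allocation. The protocol gives no alpha, power, effect size, standard deviation, number of nurses or intra-nurse correlation (ICC), so it states no precision that could be reproduced.

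**Assumptions, not in the documents.** 10 to 60 nurses; nurse ICC 0.01 to 0.10; site ICC 0.02 to 0.10; 10% missing for both nurse and tablet ratings, independent of each other. For the mean difference, the ICC is the share of the variance of the within-Veteran difference that is due to the nurse.

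**Step 1: design effect for a nurse-based mean or rate.** DE = 1 + (650/k − 1) × ICC, with k nurses. The true standard error is √DE times the naive one, and the effective sample size is 650/DE.

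| Nurses | ICC | DE | True SE / naive SE | Effective N |
|---|---|---|---|---|
| 60 | 0.01 | 1.10 | 1.05 | 592 |
| 30 | 0.01 | 1.21 | 1.10 | 539 |
| 30 | 0.05 | 2.03 | 1.43 | 320 |
| 30 | 0.10 | 3.07 | 1.75 | 212 |
| 10 | 0.10 | 7.40 | 2.72 | 88 |

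Example: 650/30 = 21.67, and 1 + 20.67 × 0.05 = 2.03.

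**Step 2: the missingness difference is affected less.** Only the nurse half of the difference is clustered. With equal rates, the variance grows by (1 + DE)/2. For 30 nurses and ICC 0.05 this is (1 + 2.03)/2 = 1.52, so the SE is too small by a factor of √1.52 = 1.23.

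**Step 3: simulation** (4,000 runs per setting, N = 650, arms crossed with nurse and site, nominal two-sided 5% test). The entries are type I error, with naive SE / true SD in brackets.

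| Result | 30 nurses, ICC 0.01 | 30 nurses, ICC 0.05 | 30 nurses, ICC 0.10 | 12 nurses, ICC 0.05 |
|---|---|---|---|---|
| Tablet minus nurse, mean | 0.07 (0.91) | 0.18 (0.69) | 0.27 (0.56) | 0.30 (0.51) |
| Tablet versus nurse, missingness | 0.06 (0.96) | 0.12 (0.80) | 0.18 (0.69) | 0.21 (0.64) |
| Overall nurse missingness rate | 0.07 (0.92) | 0.18 (0.69) | 0.28 (0.56) | 0.31 (0.51) |
| Nurse missingness, arm versus arm | 0.042 (1.02) | 0.046 (1.00) | 0.047 (1.00) | 0.051 (0.99) |

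The last row is sound because each nurse sees all three arms, so the nurse effect cancels from the arm contrast.

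**Step 4: site.** For a Veteran-reported arm contrast without a site term, type I error was 0.044 to 0.054. Adding site reduced the mean SE from 0.0959 to 0.0954 (0.5%), from 0.0954 to 0.0940 (1.5%) and from 0.0946 to 0.0914 (3.4%) at site ICC 0.02, 0.05 and 0.10.

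**The case against.** The strongest objection is that the analyses actually listed are arm against arm. Table 1 in section 5.1 has one main comparison, between the tablet arms. Section 5.3 gives missingness by arm and has no line for a tablet-minus-nurse contrast. It names covariates but does not say how standard errors are computed, and clustering methods are often left to a statistical analysis plan, which is not at hand.

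Much of this stands. It rules out several stronger readings that a reader might infer:

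- **That every interval in the trial is too narrow.** The disability outcome contains no nurse rating, and nurse missingness compared by arm keeps its error rate (step 3).
- **That omitting site biases the arm contrasts.** It does not. In the linear model it leaves some residual variance. In the logistic model it moves the odds ratio towards its marginal value without invalidating the test. Staggered site starts do not change this under individual allocation.
- **That allocation is unstratified by site.** The protocol mentions a random number generator and neither states nor excludes strata; simple randomisation would be valid in any case.

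The objection does not remove the point. The protocol is not silent here: it lists the nurse rating as a measure under a model whose rater term is fixed as tablet perception, and that is the only missingness model offered for Hypothesis 2b. Nor can a later analysis plan model the nurse if the identifier was never extracted.

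**Conclusion.** The point holds, limited to tablet-versus-nurse contrasts and overall nurse rates. For these, the model as written does not represent the rater that section 2.0 identifies as a source of variation, and standard errors that ignore the nurse will be too small.

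The size cannot be fixed from the documents. With 30 nurses and ICC 0.01 to 0.10, true type I error is about 6% to 18% for the missingness difference and 7% to 27% for the mean difference. With many nurses and a low correlation the effect is trivial (SE 1.05-fold for a nurse mean or rate at 60 nurses and ICC 0.01); with few nurses and a high one it is large (2.72-fold at 10 nurses and ICC 0.10). Section 2.0 shows that nurses differ but gives no amount, so no single figure should be quoted as the effect in this trial.

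Contrasts between randomised arms remain valid. Leaving out site costs them about 0.5% to 3.4% of the SE under the assumed site ICCs.

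**What to change.** 1. In section 5.1 (Phase 2, part A, item 5), extract the identifier of the staff member who recorded the rating, in coded form, along with the rating itself. If it is not available, extract the clinic. The protocol does not say which fields the linkage carries, so this should be checked early.
2. In the missingness row of section 5.3, name the tablet-versus-nurse contrast and its method: a nurse (or clinic) random intercept, or cluster-robust errors with a small-sample correction, since nurses may be few. Keep both ratings paired within the Veteran. The nurse effect should act on the nurse-recorded value or on the within-Veteran difference; an intercept shared by both ratings would cancel. Use the same approach for overall nurse rates and for any mean tablet-minus-nurse difference.
3. Add site as a fixed term to both models, for precision.

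No change to the allocation engine is needed. The cost is one linked field, if it exists, and an edit to two model lines. Intervals on nurse-based results will be wider, and correctly so.
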